12.4 Approximate Blood/Tissue Volumes Drawn/Collected by Trial Visit and by Sample Types

Approximate Blood Volume for Laboratory Safety Evaluations
 (Hematology and Chemistry)

Trial Visit:	Screening Visit 1	Treatment Visit 2	Treatment Visit 9	Treatment Visit 12	Treatment Visit 15/ D/C Visit
Blood Parameter	Approximate Blood Volume (mL)				
Hematology	2.00-3.00	2.00-3.00	2.00-3.00	2.00-3.00	2.00-3.00
Serum Chemistry	0.50	0.50	0.50	0.50	0.50
Serum for Free T4	0.35	N/A	N/A	N/A	N/A
Expected Total (mL)	2.85-3.85	2.85-3.85	2.85-3.85	2.85-3.85	2.85-3.85

Approximate Blood Volume for Panel of Endocrine Parameters

Trial Visit:	Screening Visit 1	Treatment Visit 2	Treatment Visit 9	Treatment Visit 10	Treatment Visit 11	Treatment Visit 12	Treatment Visit 13	Treatment Visit 14	Treatment Visit 15/ D/C Visit/ Post-Treatment
Blood Parameter	Approximate Blood Volume (mL)								
Serum Estradiol	1.00	1.00	1.00	1.00	1.00	1.00	1.00	1.00	1.00
Serum FSH	0.35	0.35	0.35			0.35			0.35
Serum LH	0.40	0.40	0.40			0.40			0.40
Serum SHBG	0.30	0.30	0.30			0.30			0.30
Serum AMH	0.35	0.35	0.35			0.35			0.35
Serum Inhibin B	0.30	0.30	0.30			0.30			0.30
Serum hCG	0.27	0.27	0.27			0.27			0.27
Calculated Free T	1.00	1.00	1.00			1.00			1.00
Total T	0.70	0.70	0.70	0.70	0.70	0.70	0.70	0.70	0.70
Expected Total (mL)	4.67	4.67	4.67	1.70	1.70	4.67	1.70	1.70	4.67

Approximate Blood Volume for Anti-MK-8962 Antibodies

[figure not shown]
Trial Visit:	Treatment Visit 2	Treatment Visit 8	Treatment Visit 9	Treatment Visit 11	Treatment Visit 12	Treatment Visit 13	Treatment Visit 15/ D/C Visit	Post-Treatment
Blood Parameter	Approximate Blood Volume (mL)							
Sampling for Anti-MK-8962 antibodies	3.00	3.00	3.00	3.00	3.00	3.00	3.00	3.00

Approximate Blood Volume for Pharmacokinetic Evaluations

Trial Visit:	Treatment Visit 2		Treatment Visit 3	Treatment Visit 4	Treatment Visit 5	Treatment Visit 6	Treatment Visit 8	Treatment Visit 9	Treatment Visit 11	Treatment Visit 12	Treatment Visit 13	Treatment Visit 15/ D/C Visit	Post-Treatment
Sample Number:	01	02	03	04	05	06	07	08	09	10	11	12	13
Blood Parameter	Approximate Blood Volume (mL)												
Pharmacokinetic sampling for MK-8962 concentration	3.00	3.00	3.00	3.00	3.00	3.00	3.00	3.00	3.00	3.00	3.00	3.00	3.00

[figure not shown]
12.5 Instructions on home-administration of MK-8962 (as provided to subjects)

Components of the MK-8962 syringe with needle

Injections should be administered in the morning once every two weeks from Visit 2 (Day 1) onwards subcutaneously into the abdominal wall. Please see the Medication Diary for detailed injection schedule.

[figure not shown]
Wash your hands thoroughly and clean the skin area where the needle will enter with a disinfectant.
Preparing the injection

[figure not shown]
Step 1:
Break the label perforation and pull off the needle-cap.
Leave the needle shield on the needle.
Place the needle shield (containing the needle) on a clean dry surface, while preparing the syringe.

[figure not shown]
Step 2:
Peel off the label on the syringe.
Hold the syringe with the grey cap pointing upwards.
Tap the syringe gently with your finger to help air bubbles rise to the top.
Check that the liquid in the syringe is clear. Do not use if it is not clear or has particles in it.

Step 3:
Keep the syringe pointing upwards.
Unscrew the syringe cap counter-clockwise.

[figure not shown]

Step 4:
Keep the syringe pointing upwards.
Screw the needle shield from Step 1 (containing the needle) clockwise onto the syringe.

[figure not shown]

Step 5:
Keep the syringe pointing upwards.
Remove the needle shield by pulling straight up and then discard the shield.
BE CAREFUL with the needle.

[figure not shown]
Injecting

Step 6:
Take the syringe between your index and middle finger, keeping the needle pointed upwards. Place your thumb on the plunger.
Carefully push the plunger upwards until a tiny droplet appears at the tip of the needle.

Step 7:
Pinch a fold of the abdomen skin between your thumb and index finger.
Insert the entire needle at a 90 degree angle into the fold of the skin.
CAREFULLY press the plunger until it cannot go any further.
Keep holding down the plunger and COUNT TO FIVE to ensure that all of the solution is injected.

Step 8:
Release your thumb from the plunger.
The needle will withdraw automatically into the syringe where it will be locked permanently.
Properly discard the used syringe into a bio-hazard container.

Note: Please record the date and time of injection on the medication diary

12.6 Tanner Staging (Male)

Pubic hair

- Tanner I -- none (prepubertal state)
- Tanner II -- small amount of long, downy hair with slight pigmentation at the base of the penis and scrotum
- Tanner III -- hair becomes more coarse and curly, and begins to extend laterally
- Tanner IV -- adult-like hair quality, extending across pubis but sparing medial thighs
- Tanner V -- hair extends to medial surface of the thigh

Genitals

- Tanner I -- prepubertal (testicular volume less than 1.5 ml; small penis)
- Tanner II -- testicular volume between 1.6 and 6 ml; skin on scrotum thins, reddens and enlarges; penis length unchanged
- Tanner III -- testicular volume between 6 and 12 ml; scrotum enlarges further; penis begins to lengthen
- Tanner IV -- testicular volume between 12 and 20 ml; scrotum enlarges further and darkens; penis increases in length and circumference
- Tanner V -- testicular volume greater than 20 ml; adult scrotum and penis

12.7 Blood Pressure and Anthropometric Measurements

Blood Pressure

Ensure patient has not had any caffeine or tobacco within 30 minutes. BP should be measured in the sitting position. The patient will remain in the sitting position for at least 5 minutes before any blood pressure readings are recorded. The same arm, preferably the non-dominant arm, should be used for all blood pressure determinations at each visit. Systolic and diastolic BP will be determined by obtaining two measurements, 1 to 2 minutes apart. The consecutive systolic BP readings should be within 5 mm Hg of each other and the consecutive diastolic BP readings should be within 5 mm Hg of each other. The final BP measurement must be recorded.

Weight

Weight will be taken on the same calibrated digital scale throughout the study, after voiding and while wearing only a gown and underwear (no street clothes, no shoes or socks). Subjects should step gently onto the scale, place both feet together in the center of the scale and stand straight with eyes directed ahead. **Subjects should be instructed to stand still and not sway. Measurement will be recorded after the weight has stabilized.**

Weight will be measured after voiding (to the nearest 0.2 kg). Measurements will be collected until 2 consecutive measurements do not differ by more than 0.2 kg from each other. The final weight measurement must be recorded. The same digital scale must be used throughout the study.

The SPONSOR will provide a scale and/or 10-kg certified weight to study sites that do not have them. **The scale must be calibrated according to the manufacturer's instructions at set-up and when it is transferred or moved. Additional calibration should be performed according to the manufacturer's instructions.**

Height

Standing height will be measured without shoes using a stadiometer.

Standing height will be assessed through maximum vertical stature for persons who can stand unassisted. Hair ornaments, barrettes, braids, jewelry, or cornrows should be moved or removed from the top of the head before the measurement is taken.

A fixed stadiometer with vertical backboard, fixed floorboard and movable headboard must be used. Subjects should stand with the heels of their feet against the vertical backboard with feet pointing outward at approximately a 60-degree angle. Body weight should be distributed evenly with both feet flat on the floor. The examiner should check several contact points with the vertical backboard, including heels, buttocks, shoulder blades, and the back of the head. This may be difficult for subjects with certain body shapes. However, the head should be in the Frankfort plane (an imaginary line from the ear canal to just below the lower orbit of the eye should be parallel to the floor). Subject should be looking straight ahead, and be asked to take a deep breath and stand tall. Once the subject is positioned, the headboard will be placed on top of the head, with sufficient pressure to compress the hair. The measurement is

recorded in cm, to the nearest mm. **Measurements will be collected until 3 consecutive measurements do not differ by more than 1.0 cm from each other. The final height measurement must be recorded.** Some patients may have physical conditions that may limit the ability to measure height accurately (e.g., kyphosis). In such cases, height should be measured to the best of the examiner's ability, a note should be made of the condition and measurements should be repeated in the same manner for the rest of study.

The stadiometer must be calibrated upon mounting the stadiometer to the wall, and according to the manufacturer's instructions thereafter.

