Treatment with MK-8962			Once every two weeks (first dose on Day 1/Week 0 and last dose on Day 435 /Week 62)																						
Dispense hCG ^l									X	X		X		X		X		X		X		X			
Treatment with hCG											Twice weekly (e.g., every Monday and Thursday, or every Tuesday and Friday) ^m														
Clinical Procedures/Assessments																									
Full Physical Examination	X																						X	X	
Focused Physical Examination ⁿ		X								X							X								
Vital Signs (HR, BP measured twice)	X	X							X							X							X	X	
Weight (measured twice)	X	X					X	X		X	X		X		X			X		X		X	X		
Height for Growth Velocity (measured 3 times)	X	X							X						X								X	X	
Testicular ultrasound ^o	X	(X) ^t							X						X							X	X ^p	(X) ^p	
Tanner Staging ^q	X	X							X						X							X	X		
Adverse Events Monitoring	X	X	X	X	X	X	X	X	X	X	X	X	X	X	X	X	X	X	X	X	X	X	X		

Trial Period:		MK-8962 Priming Phase									Combined Treatment Phase (MK-8962 / hCG) ^a														
		1	2	3	4	5	6	7	8	9	10		11		12		13		14		15	D/C ^b	Follow-up ^c		
Visit Number																									
Visit/Contact Title:	Screening	Treatment Allocation								TC		TC		TC		TC		TC		TC		D/C ^b			
Scheduled Week ^d :	-1	0	1	1	1	2	2	4	8	12	16	20	24	28	32	36	40	44	48	52	56	60	64 ^e		
Scheduled Study Day:	-7 to -1	1 ^f	3	5	8	11	15	29	57	85	113	141	169	197	225	253	281	309	337	365	393	421	449		+7 ^c
Scheduling Window (Days):	-42 to -1								+/- 7	+/- 3	+/- 7	+/- 3	+/- 7	+/- 3	+/- 7	+/- 3	+/- 7	+/- 3	+/- 7	+/- 3	+/- 7	+/- 7	+/- 7	+/- 7	+24
Laboratory Procedures/Assessments																									
Serum for free T4	X																								
Hematology	X	X								X							X						X	X	
Chemistry Panel	X	X							X							X							X	X	
Serum for endocrine parameters ^r : FSH, LH, hCG, inhibin-B, AMH, Calc. Free T, and SHBG	X	X								X							X						X	X ^p	(X) ^p
Serum for endocrine parameters ^r : Total T and E2	X	X								X	X		X			X			X		X		X	X ^p	(X) ^p
Pharmacokinetic (PK) sampling for MK-8962 concentration ^s		see Section 7.1.3.3.1 Flow Chart for Pharmacokinetic Assessments																							
Sampling for Anti-MK-8962 antibodies ^r		X							X	X			X			X			X			X	X	X	

AMH = anti-Müllerian hormone; E2 = estradiol; FSH = follicle stimulating hormone; hCG = human chorionic gonadotropin; HIV = human immunodeficiency virus; LH = luteinizing hormone; SHBG = sex hormone-binding globulin; TC = telephone call; T = testosterone

^a The Combined Treatment Phase starts at the end of Week 12.

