7.1.2.2 Vital Signs, Height, and Weight

Vital signs (including HR and BP), body weight and height will be obtained at screening and at subsequent visits specified in the Trial Flow Chart (Section 6.0).

BP and *HR* will be measured (to be performed in duplicate) using an electronic blood pressure monitor.

Body weight will be measured (to be performed in duplicate) using a calibrated digital scale.

Height will be measured (to be performed in triplicate) using a wall-mounted calibrated stadiometer. The Sponsor will calculate growth velocity of height based on these measurements.

For details on measuring techniques, refer to Section 12.7.

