8.4.1 Efficacy/Immunogenicity/Pharmacokinetics Endpoints

Primary Efficacy Endpoint

The primary efficacy endpoint for this trial is the Change from Baseline (Day 1) to Week 64 in log-transformed testicular volume (measured as the sum of volumes of left and right testes by ultrasound).

Secondary Efficacy Endpoint

- Change from baseline in serum inhibin B concentrations at Week 64;
- Growth velocity at Week 36 and Week 64;
- Tanner Stage of pubertal development at Weeks 12, 36 and 64.
- Characterization of MK-8962 pharmacokinetics (based on serum MK-8962 concentrations) through 64 weeks of treatment.

- Characterization of testicular sonographic pattern reflecting pubertal development through 64 weeks of treatment;
- Changes from baseline in endocrine parameters (LH, calculated free testosterone, Total T, E2, SHBG, and AMH at Weeks 12, 36 and 64;

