8.6.1.2 Secondary Efficacy Analysis

The change in serum inhibin B concentrations after 64 weeks will be summarized. In addition, changes from Day 1 to Week 12, and from Week 12 to Week 64 will also be summarized. A listing by subject and time point will also be provided for each treatment phase.

The growth velocity (cm/year) will be summarized as follows:

For each subject, the growth velocity over the 36 and 64 week treatment periods will be extracted using the slopes estimated from an overall mixed random intercept and random slope model of height (cm) and time (in years) and age as covariates. Overall growth velocity slope over 36 and 64 weeks will also be presented based on the same model. An unstructured covariance matrix will be used to model the correlation among repeated measurements. In the event of model convergence issues, other covariance structures (i.e. AR or compound symmetry) will be considered.

In addition, growth in cm over 12, 36 and 64 weeks will be listed for each age (14, 15, 16 and 17 years of age at randomization). Annualized growth velocity (cm/year) at 36 and 64 weeks will also be calculated and listed.

For each male subject, Tanner Staging will be recorded for both pubic hair and testicular volume. Tanner Stage of development at Baseline, week 12, week 36 and at the end of the 64 weeks of combined treatment will be summarized by shift table. A listing of Tanner Stage by time point and subject will also be provided.

Descriptions of sonographic testicular patterns will be listed at Baseline and weeks 12, 36 and 64. Any changes over time will be described.

For continuous variables, summary statistics will include the number of observations, mean, standard deviation, median, minimum and maximum. For categorical variables, frequency distributions will be provided.

Serum concentrations of hormones (LH, Total T, E2, SHBG, and AMH) will be summarized by assessment (Week 1-64). Additional summary statistics will include first and third quartile as well as geometric mean together with coefficient of variation. Values below the Lower Limit of Quantification (LLOQ) will be set to $\frac{1}{2}$ times the LLOQ for the calculation of descriptive statistics. The number and percentage of values below the LLOQ will be reported. Additionally, serum hormone concentrations will be summarized by treatment phase.

The summary of the key efficacy analyses is provided in [Table 6](#).

Table 6 Analysis Strategy for Key Efficacy Variables

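### Height is read three times but Section 12.7 requires only the final reading to be recorded, and no visit height is defined; using one reading could raise the measurement-error SD of growth velocity up to about 1.7-fold.

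*Combined protocol and SAP*

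**What the plan says.** Three places describe how height is obtained. The flow chart (Section 6.0) lists "Height for Growth Velocity (measured 3 times"). Section 7.1.2.2 says "Height will be measured (to be performed in triplicate) using a wall-mounted calibrated stadiometer" and continues "The Sponsor will calculate growth velocity of height based on these measurements". Section 12.7, the measuring instruction that sites follow, says "Measurements will be collected until 3 consecutive measurements do not differ by more than 1.0 cm from each other" and then "The final height measurement must be recorded". Readings are "recorded in cm, to the nearest mm".

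The endpoint in Section 8.4.1 is "Growth velocity at Week 36 and Week 64". In Section 8.6.1.2 "the growth velocity over the 36 and 64 week treatment periods will be extracted using the slopes estimated from an overall mixed" model with random intercept and random slope. The same section adds listings of growth in cm over 12, 36 and 64 weeks by age, and of annualized velocity at 36 and 64 weeks.

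Neither the protocol nor its SAP section says whether the last reading, the mean or the median is the height for a visit.

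**The concern.** Sections 7.1.2.2 and 12.7 do not fit together. The first describes a calculation from triplicate readings. The second obliges the site to keep one. If a site does only what 12.7 demands, the Sponsor receives a single reading and cannot average. The supplemental SAP allowed for in Section 8.0 could settle the derivation later, but not restore readings that were never written down.

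The tolerance gives this some weight. Section 12.7 reads weight to 0.2 kg and requires agreement within 0.2 kg, which is one recording unit. Height is read to 1 mm and needs agreement only within 1.0 cm, which is ten recording units, so accepted height readings may differ appreciably.

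At stake is the precision of a secondary endpoint in about 15 enrolled boys, of whom 10 are expected to complete. The annualized velocities are listed per boy. There, measurement error is not averaged over subjects and is magnified by division by a short interval, most of all at Week 36.

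**Working it through.** The documents give no measurement-error SD and no precision figure for height, so there is no stated figure to reproduce. The SDs and correlations below are assumptions, shown as ranges.

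**Inputs from the documents.** Three readings per visit (6.0, 7.1.2.2); repeat until three consecutive readings lie within 1.0 cm (12.7); resolution 0.1 cm (12.7); Week 36 is Day 253 and Week 64 is Day 449 (6.0), so 252 and 448 days after Day 1.

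**Upper bound.** Let ρ be the share of error variance common to all readings at a visit. If the repeat rule never triggers, the ratio of error SD, last reading to mean of three, is 1/√(ρ + (1 − ρ)/3).

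- ρ = 0: √3 = 1.73
- ρ = 0.25: 1.41
- ρ = 0.5: 1.22
- ρ = 0.75: 1.10

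**From height error to velocity error.** For two visits, velocity error SD = √2 × SD / years.

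- Week 36: √2 / (252/365.25) = 1.414/0.690 = 2.050 per cm
- Week 64: √2 / (448/365.25) = 1.414/1.227 = 1.153 per cm

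**Effect of the 1.0 cm rule.** I simulated readings rounded to 0.1 cm and repeated until the last three agreed within 1.0 cm, then compared the last reading with the mean of those three. Errors are independent (ρ = 0).

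| Assumed single-reading SD (cm) | First three readings pass | Ratio | Week 36, last vs mean (cm/yr) | Week 64, last vs mean (cm/yr) | Fall in error variance with the mean |
|---|---|---|---|---|---|
| 0.2 | 99.9% | 1.73 | 0.414 vs 0.239 | 0.233 vs 0.135 | 67% |
| 0.3 | 96% | 1.62 | 0.590 vs 0.364 | 0.332 vs 0.205 | 62% |
| 0.4 | 85% | 1.44 | 0.721 vs 0.499 | 0.405 vs 0.281 | 52% |
| 0.5 | 70% | 1.31 | 0.833 vs 0.635 | 0.469 vs 0.357 | 42% |

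For example, at SD 0.3 the accepted last reading has error SD 0.288 cm and the mean of three 0.178 cm. Then 0.288 × 2.050 = 0.59 and 0.178 × 2.050 = 0.36 cm/yr at Week 36. The ratio falls as the SD rises because the rule increasingly discards extreme readings.

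With half the error variance shared within a visit (ρ = 0.5), the ratio is 1.23 at within-visit SD 0.2, 1.19 at 0.3 and 1.09 at 0.5.

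**A bound that needs no SD.** If two accepted readings are equal and the last is 1.0 cm away, the last differs from the mean of three by 1.0 − 0.33 = 0.67 cm. In opposite directions at two visits, this moves a boy's velocity by 1.33/0.690 = 1.9 cm/yr at Week 36 and 1.33/1.227 = 1.1 cm/yr at Week 64. This is an extreme that the written rule permits, not an expected error.

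**Mixed-model slopes.** A straight-line slope through the five height visits (screening, Day 1, Weeks 12, 36 and 64) has error SD 0.941 per cm, against 1.153 for two points. That is 18% less (0.941/1.153 = 0.82), before any shrinkage.

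**Share of total variation.** Suppose the true between-boy SD of velocity is 1 to 3 cm/yr and the single-reading SD 0.2 to 0.5 cm, with independent errors and the repeat rule ignored. Using one reading instead of the mean then raises the total SD of two-point velocity by 0.2% to 10% at Week 64 and 0.6% to 23% at Week 36. The upper ends need SD 0.5 cm, where ignoring the repeat rule overstates the effect.

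**The case against.** The strongest reply is that the loss of readings is not shown. Section 12.7 says the final height must be recorded; it does not say that only this one may be, and it tells no one to discard the others. Section 7.1.2.2 refers to the measurements in the plural directly after requiring triplicate. The eCRF layout is not in the documents, and Section 10.6 leaves data-management detail to a separate document. This stands: the documents support saying that two readings may be lost, not that they are.

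A reader might also infer that growth velocity simply carries 1.7 times the necessary error, or that averaging always cuts error variance by two thirds. The documents support neither. Both figures are ceilings that need independent errors, a repeat rule that almost never triggers, and analysis of the last reading alone. Errors shared within a visit, such as time of day, posture or observer, are not reduced by averaging. The 1.0 cm rule itself narrows the gap.

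Third, the main growth analysis is a multi-visit mixed model, not a two-point difference, and the endpoint is descriptive in an estimation study with no hypothesis test. This too stands and limits the consequence.

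Last, keeping a final value after an agreement check is applied alike to blood pressure, weight and height in Section 12.7. That shows a consistent convention. It does not reconcile the convention with 7.1.2.2 or define the visit height.

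**Conclusion.** The point holds as a cheap improvement. Sections 7.1.2.2 and 12.7 are at best ambiguous together, Section 8.6.1.2 leaves the visit height undefined, and a site following 12.7 literally may fail to keep two readings already taken.

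If only the last reading is analysed, the measurement-error SD of growth velocity is up to about 1.7 times that from the mean of three. Under the repeat rule with independent errors it is about 1.6 times at an assumed SD of 0.3 cm and about 1.3 times at 0.5 cm, and less with errors shared within a visit. These factors concern measurement error only; the effect on total variation between boys is smaller. The loss matters most for the annualized velocities listed per boy, above all at Week 36, and less for the model slopes. The primary endpoint and the sample size are unaffected.

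**What to change.** In Section 12.7, require all three accepted height readings to be entered in the eCRF. In Section 8.6.1.2, state that their mean is the visit height for every growth-velocity calculation, both the mixed model and the listings. Align Section 7.1.2.2 with this wording.

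The cost is two extra eCRF fields per height visit and a short text change. No procedure is added, because the readings are already taken. The recording change needs to come before data collection, since it cannot be made good afterwards.
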